9.3 Selection of Study Population

Approximately 1500 subjects who have self-reported insomnia will be screened to provide 900 randomized subjects in North America, South America, Europe, Asia, and Oceania. Subjects who do not meet all of the inclusion criteria or who meet any of the exclusion criteria will not be eligible to receive study drug.

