9.7.1 Statistical and Analytical Plans

The statistical analyses are described in this section. Further details of the analytical plan will be provided in the SAP which will be finalized before database lock and treatment unblinding.

All statistical tests will be based on the 5% level of significance (2-sided).

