9.7.2 Determination of Sample Size

The sample size was estimated for the comparison of LEM10 and LEM5 with PBO, with respect to the mean change from Study Baseline at the end of Month 6 of the mean sSOL, the mean sSE and mean sWASO. This estimate was based on sequential gate-keeping procedure at the 0.05 α -level as described above. There is sufficient power for both the primary endpoint (sSOL) and key secondary endpoints (sSE and sWASO).

On the basis of the dose finding study E2006-G000-201 (Study 201) for the lemborexant total summaries at Days 8 to 15, the standard deviation of change from Study Baseline for sSOL is assumed to be 33 minutes, for sSE is assumed to be 12% and for sWASO is assumed to be 43 minutes. The LS mean treatment differences at Days 8 to 15 from Study 201 were as follows: for sSE 9.5% for LEM10 and 5.5%, for LEM5; for sWASO -26.6 minutes for LEM10, and -11.3 minutes for LEM5. As a result of the non-normal distribution of sSOL, the LS mean treatment difference is not available (geometric mean ratios were used). Therefore, estimating treatment difference using medians at Days 8 to 15 from Study 201, leads to a median treatment difference of approximately -6.8 minutes for LEM10. For LEM5, a median treatment difference is approximately -13.2 minutes.

To detect a treatment difference in sSOL of at least -8.7 minutes, a sample size of 300 per treatment group at 5% (2-sided) level of significance has >90% power for comparing a dose of lemborexant with PBO.

To detect a treatment difference in sSE of at least 5.5%, a sample size of 300 per treatment group at 5% (2-sided) level of significance has >99% power for comparing a dose of lemborexant with PBO.

For sWASO, total 900 subjects (300 per treatment group) will give 90% power to detect a difference of -11.4 minutes for LEM5 and LEM10 compared to PBO (Table 4). The study is adequately powered to show the statistically significant difference from PBO for LEM10 as well as for LEM5.

Table 4 Sample Size Calculations for Study E2006-G000-303

Alpha=0.05	Difference between Active and Placebo CFB (min)	Power = 80%		Power =90%	
		Sample size per group	Overall group sample size	Sample size per group	Overall group sample size
sSOL (SD=33)	-6.8	371	1113	496	1488
	-7.6	300	900	398	1194
	-8	269	807	359	1077
	-8.7	229	687	300	900
	-9	213	639	284	852
	-10	172	516	230	690
	-11	143	429	191	573
sWASO (SD=43)	-9	360	1080	481	1443
	-9.9	300	900	398	1194
	-10	292	876	390	1170
	-11	241	723	323	969

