	-11.4	225	675	300	900
	-12	203	609	271	813

CFB = change from baseline, sSOL = subjective sleep onset latency, sWASO = subjective wake after sleep onset.

The study also has adequate power for the secondary analysis of responders. A sleep onset responder is defined as follows: sSOL at Study Baseline is ≥ 30 minutes and mean sSOL at 6 months is ≤ 20 minutes, and a sleep maintenance responder is defined as follows: sWASO at Study Baseline is ≥ 60 minutes and mean sWASO at 6 months is ≤ 60 minutes and shows a reduction of >10 minutes compared to Study Baseline. A total of 900 subjects gives $>99\%$ power to detect a treatment difference in sleep onset responder rates of 16% and sleep maintenance responder rates of 24.4%.

The above sample size also meets regulatory safety requirements. Even with early discontinuation rates as high as 50% at Month 6 (ie, 150 subjects remaining) and 60% by Month 12 (ie, 120 subjects remaining in each treatment group), the requirement for 100 subjects in each of the elderly and non-elderly age-groups to complete 12-months of treatment on 5 or 10 mg lemborexant will be met. In addition, 420 total subjects would have completed 6 months of treatment of 5 mg or 10 mg lemborexant.

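### The 90% power figures for sSOL and sWASO assume Month 6 data from all 300 subjects randomised per arm; no allowance for missing data is stated

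*Protocol*

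**What the plan says.** Protocol 9.7.2 sizes the trial on the change from Study Baseline at the end of Month 6. The SDs come from the Phase 2 dose-finding study: "the standard deviation of change from Study Baseline for sSOL is assumed to be 33 minutes, for sSE is assumed to be 12" percent, and 43 minutes for sWASO. The power statements are:

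- sSOL: power is given as above 90%, in the sentence that begins "To detect a treatment difference in sSOL of at least -8.7 minutes, a sample size of 300 per treatment group at 5% (2-sided) level of".
- sWASO: "For sWASO, total 900 subjects (300 per treatment group) will give 90% power to detect a difference of -11.4 minutes for LEM5 and LEM10" against placebo.
- sSE: "To detect a treatment difference in sSE of at least 5.5%, a sample size of 300 per treatment group", with power given as above 99%.

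Table 4 lists exactly 300 per group (900 overall) at 90% power for -8.7 and -11.4 minutes. The text then calls the study adequately powered for both doses.

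The same 900 is the number randomised. Protocol 9.3 says that about 1500 subjects "will be screened to provide 900 randomized subjects", 9.4.3 allocates them about 1:1:1, and 9.5.5 says that removed subjects are not replaced.

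The only attrition figures are in the last paragraph of 9.7.2, which checks the safety counts: "Even with early discontinuation rates as high as 50% at Month 6 (ie, 150 subjects remaining"), then 60% by Month 12. SAP section 2 repeats all of this. The protocol synopsis repeats the power statements without the safety paragraph.

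**The concern.** The number needed for 90% power equals the number randomised, so the efficacy calculation has no allowance for subjects without a Month 6 value. The same section tests the sample against heavy discontinuation for safety counts and treats it as loss-free for efficacy.

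Missing Month 6 values are foreseen. SAP 6.1.1 sets a diary week to missing when fewer than 4 of 7 nights are available, and SAP Table 5 lists the monotone missing patterns used for imputation.

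sSOL is tested first in the fixed sequence and sWASO last. A failed sSOL step stops all later tests, so an overstated sSOL power affects the whole hierarchy.

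**Working it through.** **Inputs.** Two-sided alpha 0.05 (protocol 9.7.1: "All statistical tests will be based on the 5% level of significance (2-sided")), with the full 0.05 at each step of the sequence. SD 33, 43 and 12; differences 8.7, 11.4 and 5.5; 300 randomised per arm (all 9.7.2). The loss rates of 10%, 20% and 30% are illustrative assumptions. The 50% is the bound in 9.7.2, read here as the share with no Month 6 data.

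**Method.** Unadjusted comparison of two means with n per arm:

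- standard error = SD × √(2/n)
- noncentrality = difference / standard error
- power = probability that a noncentral t on 2n − 2 df exceeds the two-sided 5% critical value

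**Step 1: reproduce the plan at n = 300.** The critical value is 1.964.

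- sSOL: standard error 33 × √(2/300) = 2.694; noncentrality 8.7/2.694 = 3.229; power 89.7% (normal approximation 89.8%). Reaching 90% takes 303 per arm by the normal approximation.
- sWASO: standard error 43 × √(2/300) = 3.511; noncentrality 11.4/3.511 = 3.247; power 90.0% (normal approximation 90.1%; 299 per arm needed).
- sSE: 99.99%.

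Every row of Table 4 reproduces to within 3%. The plan's figures are therefore the powers of an unadjusted two-sample comparison with 300 observed per arm. For sSOL the result is about 90%, not above it.

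**Step 2: reduce n to 300 × (1 − share without Month 6 data).**

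| Share without Month 6 data | n per arm | sSOL -8.7 | sWASO -11.4 |
|---|---|---|---|
| 0% | 300 | 89.7% | 90.0% |
| 10% | 270 | 86.4% | 86.8% |
| 20% | 240 | 82.2% | 82.6% |
| 30% | 210 | 76.9% | 77.4% |
| 50% | 150 | 62.4% | 62.9% |

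sSE at 5.5% still has 97.7% power at 150 per arm.

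**Step 3: side checks, each on an assumption the documents do not supply.**

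- Baseline adjustment: multiply the SD by √(1 − r²), where r is the correlation of baseline with change. At 10% loss, r = 0.3, 0.4 and 0.5 gives sSOL/sWASO power of 89/90%, 92/92% and 94/94%. At 20% loss it gives 86/86%, 88/89% and 91/92%.
- Dilution: suppose all 300 are observed, but a share of the active arm is off drug with no remaining benefit. With 10% off drug the sSOL difference becomes 8.7 × 0.9 = 7.83 minutes and power is about 83%. With 20% it becomes 8.7 × 0.8 = 6.96 minutes and power is about 73%.

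**The case against.** The strongest reply is that stopping drug is not the same as missing Month 6 data. The 50% is an upper bound used to check safety exposure, not an expected rate. Subjects who stop are encouraged to keep the diary and attend visits (protocol 9.5.5), and their data are used (9.7.1.6). The primary analysis also adjusts for baseline, region and age group, and imputes from earlier visits. All of this stands. A reader might infer that the trial really has about 62% power, or that 90% is shown not to be delivered. The documents support neither, because they give no rate of missing Month 6 data. Nor do they show that every missing value takes power below 90%: Step 3 shows that a strong enough baseline correlation could offset 10% or 20% loss.

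A reader might also infer that the claim of adequate power fails for every comparison unless data are complete. It does not. At 150 per arm, the Phase 2 differences of -13.2 minutes for sSOL (LEM5) and -26.6 minutes for sWASO (LEM10) keep 93.2% and 99.96% power, and sSE keeps 97.7%. Table 4 also prints the sizes for 80% power, 229 for sSOL and 225 for sWASO. Losses of 71/300 = 24% and 75/300 = 25% would therefore still leave about 80%. The lack of headroom is at the 90% level only.

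These mitigations do not make the stated figures right. The plan quantifies none of them. Off-drug data restore the count but may dilute the effect, so the worst-case row is not a floor. And the printed 90% is reproduced only by the unadjusted calculation with 300 observed per arm.

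**Conclusion.** The point holds as an unstated assumption behind two power figures. Nothing in Table 4 is materially miscalculated. By the plan's own method, sSOL at -8.7 minutes has 89.7% power and sWASO at -11.4 minutes has 90.0% only if all 300 randomised per arm contribute Month 6 data. The sSOL statement of more than 90% is slightly too high even then. With 10% to 30% of subjects lacking Month 6 data, power runs from about 86/87% down to 77/77%. At 50% it is 62/63%, the case in which every discontinuer at the plan's bound lacks Month 6 data.

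These figures rest on the documents' SDs and differences, an unadjusted comparison, and no recovery of information from retrieved data, imputation or covariates. They are in raw minutes, as in 9.7.2, whereas SAP 3.4.1 analyses log-transformed sSOL. They therefore show how the stated power responds to loss on the planning scale, not the power of the final sSOL test. The conclusion is confined to the -8.7 and -11.4 minute differences.

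**What to change.** In protocol 9.7.2, the sample size rationale of the synopsis, and SAP section 2:

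1. State that the sSOL and sWASO power figures assume 300 subjects per arm with Month 6 data and include no attrition allowance. Give sSOL as about 90%, not above 90%.
2. Add power by share of subjects without Month 6 data (sSOL/sWASO): about 86/87% at 10%, 82/83% at 20%, 77/77% at 30% and 62/63% at 50%, with sSE at 97.7% or more. Label the range illustrative because no expected rate is available, and the 50% row a worst case in which every discontinuer lacks Month 6 data.
3. Note that retrieved data, imputation and baseline adjustment may recover some power, that off-drug data may dilute the effect, and that the figures are in raw minutes although sSOL is analysed on the log scale. Give no upper limit for recovery, since the documents provide no basis for one.
4. Qualify the claim of adequate power for the -8.7 and -11.4 minute differences accordingly.

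The cost is text only. The stated power becomes less favourable, no analysis changes and no enrolment is added.

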- The study will begin enrollment in approximately November 2016 (revised per Amendments 01 and 03)
- The estimated duration for each subject on study is anticipated to be a maximum of 60 weeks (a maximum 35-day Prerandomization Phase [that includes a Screening Period, a maximum 17-day Run-In Period, and a Baseline Period] + 52 weeks of the Randomization Phase + a 1-week window + a 2-week Follow-Up Period). (revised per Amendment 03)
- Approximately 900 subjects with insomnia disorder (18 years or older) will be randomized to receive LEM5 or LEM10 or PBO for 6 months. After 6 months, subjects who previously received lemborexant will continue to receive lemborexant at the same dosage level for an additional 6 months, while subjects who previously received PBO will undergo a 2nd randomization to receive LEM5 or LEM10 for 6 months.

Number of Subjects

Approximately 1500 subjects will be screened to provide 900 randomized subjects.

Inclusion Criteria

1. Male or female, age 18 years or older at the time of informed consent
2. Meets the Diagnostic and Statistical Manual of Mental Disorders, Fifth Edition (DSM-5) criteria for Insomnia Disorder, as follows:
 - Complains of dissatisfaction with nighttime sleep in the form of difficulty getting to sleep, difficulty staying asleep and/or awakening earlier in the morning than desired despite adequate opportunity for sleep
 - Frequency of complaint ≥ 3 times per week
 - Duration of complaint ≥ 3 months
 - Associated with complaint of daytime impairment
3. At Screening: History of sSOL ≥ 30 minutes on at least 3 nights per week in the previous 4 weeks AND/OR sWASO ≥ 60 minutes on at least 3 nights per week in the previous 4 weeks (revised per Amendment 03)
4. At Screening: Reports regular time spent in bed, either sleeping or trying to sleep, between 7 and 9 hours
5. At 1st Screening Visit (Visit 1) and 2nd Screening Visit (Visit 2a): Reports regular bedtime, defined as the time the subject attempts to sleep, between 21:00 and 01:00 and regular waketime, defined as the time the subject gets out of bed for the day, between 05:00 and 10:00 (revised per Amendment 03)
6. At Screening and Study Baseline: ISI score ≥ 15

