22. Used any prohibited prescription or over-the-counter medications within 1 week or 5 half lives, whichever is longer, before the 1st dose of study medication (Run-In Period). (A list of prohibited or limited concomitant medications is presented in [Appendix 3](#) of the protocol.)
23. Used any modality of treatment for insomnia, including cognitive behavioral therapy or marijuana, within 1 week or 5 half lives, whichever is longer, before the 1st dose of study medication (Run-In Period)
24. Failed treatment with suvorexant (efficacy or safety) following treatment with an appropriate dose and of adequate duration in the opinion of the investigator
25. Transmeridian travel across more than 3 time zones in the 2 weeks before Screening, or between Screening and Study Baseline
26. A positive drug test at Screening, Run-In, or Baseline or unwilling to refrain from use of recreational drugs during the study
27. Hypersensitivity to the study drug or any of the excipients
28. Currently enrolled in another clinical trial or used any investigational drug or device within 30 days or 5 times the half-life, whichever is longer preceding informed consent
29. Previously participated in any clinical trial of lemborexant

Study Treatments

LEM5, LEM10, or lemborexant-matched PBO taken orally in tablet form each night immediately before the time the subject intends to try to sleep

Run-In Period

All subjects will receive 1 lemborexant-matched PBO in a single-blind manner during the Run-In Period immediately before the time the subject intends to try to sleep.

Randomization Phase (Periods 1 and 2)

During Period 1 (Day 1 through end of Month 6), all subjects will receive 1 tablet as described below, according to the treatment arm to which the subject has been randomized:

- LEM5: 1 lemborexant 5-mg tablet
- LEM10: 1 lemborexant 10-mg tablet

- PBO: 1 lemborexant-matched PBO tablet

During Period 2 (Month 7 through 12), all subjects will receive 1 tablet as described below, according to the treatment arm to which the subject has been randomized

- LEM5: 1 lemborexant 5-mg tablet
- LEM10: 1 lemborexant 10-mg tablet

Duration of Treatment

A maximum of approximately 55.5 weeks: Up to 17 days of PBO during the Run-In Period and up to 52 weeks of randomized treatment.

Concomitant Drug/Therapy

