9 INVESTIGATIONAL PLAN

9.1 Overall Study Design and Plan

This study is a 12-month, multicenter, randomized, controlled, double-blind, parallel-group study of 2 doses of lemborexant in approximately 900 male or female subjects with insomnia disorder (subjects who complain of difficulties with sleep onset and/or sleep maintenance). Approximately 40% of the population will be 65 years of age or older. Note: enrollment of subjects <65 years may be limited if the percentage of enrolled subjects ≥ 65 years is below expectations toward the end of the study. (revised per Amendments 01 and 03)

The study will have 2 phases, the Prerandomization Phase and the Randomization Phase. The Prerandomization Phase will comprise 3 periods and last up to 35 days: a Screening Period, a Run-In Period and a Baseline Period. The Randomization Phase will comprise a 6-month, placebo-controlled treatment period (Period 1). During the next 6 months (Period 2), subjects will receive only active treatment. Subjects will be informed that they will receive PBO at some point during the study and that all will receive active drug for at least 6 months. They will not be informed of either the timing of these periods or the timing of the 2nd randomization. A 2-week Follow-Up Period will then take place, followed by an End of Study Visit. (revised per Amendment 03)

End of Study

The end of the study will be the date of the last study visit for the last subject. As required by some regulatory agencies, the following estimates are provided:

- The study will begin enrollment in approximately November 2016 (revised per Amendments 01 and 03)
- The estimated duration for each subject on study is anticipated to be a maximum of 60 weeks (a maximum 35-day Prerandomization Phase [that includes a Screening Period, a maximum 17-day Run-In Period, and a Baseline Period] + 52 weeks of the Randomization Phase + a 1-week window + a 2-week Follow-Up Period). (revised per Amendment 03)
- Approximately 900 subjects with insomnia disorder (18 years or older) will be randomized to receive LEM5 or LEM10 or PBO for 6 months. After 6 months, subjects who previously received lemborexant will continue to receive lemborexant at the same dosage level for an additional 6 months, while subjects who previously received PBO will undergo a 2nd randomization to receive LEM5 or LEM10 for 6 months.

An overview of the study design is presented in [Figure 1](#).

[figure not shown]

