- d: Visits 4, 5, and 6 are to be conducted within ± 4 days of the schedule. Visits 7 through 15, and EOS to be done within ± 7 days of the schedule. (revised per Amendments 01 and 03)
- e: The site will telephone the subject to assess AEs, to record concomitant medications and to review the sleep diaries. If any AE is clinically significant and requires follow-up, a clinic visit should be arranged (Unscheduled Visit).
- f: The Run-In Period may start between Day -17 and Day -14 and must continue for approximately 14 consecutive days and a maximum of 17 days. (revised per Amendment 01)
- g: Defined as a calendar month.
- h: Inclusion and exclusion criteria to be evaluated at visits other than or in addition to Visit 1 are listed in [Appendix 2](#) (revised per Amendment 01).
- i: Sleep Disorders Screening Battery comprises: STOPBang, International Restless Legs Scale, and Epworth Sleepiness Scale. (revised per Amendments 01 and 03).
- j: A full physical examination will be carried out at Screening and EOS (ET at the discretion of the investigator) and will include a brief neurological examination. A brief physical examination will be carried out at other visits.
- k: The ECG should be repeated if an abnormality is observed.
- l: If subject has a normal ECG baseline reading, but during any visit thereafter the QT is measured as >450 ms, 3 consecutive ECGs separated by 5 to 10 minutes will be performed to confirm the abnormality.
- m: Female subjects of child-bearing only.
- n: Urine drug test to be conducted at Unscheduled Visits at the discretion of the investigator and at ET only for subjects who withdraw because of an Adverse Event.
- o: Viral screening for hepatitis B (HBsAg) and hepatitis C (HCV antibody IgG) will be conducted.
- p: Clinical laboratory tests include hematology, blood chemistry, and urinalysis.
- q: Subjects should complete the Sleep Diary, within 1 hour of waketime, each day throughout the study until EOS. Sleep diaries should be reviewed for eligibility: for the 7 consecutive days immediately before Visit 2, and for the Run-In Period at Visit 3. Thereafter, the Sleep Diary should be reviewed for completeness

-
- once a month. (revised per Amendment 03)
- r: Study drug compliance (tablet count) will be carried out at each clinic visit from Visit 3a through Visit 15. (revised per Amendments 01 and 03)

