9.7.1.8.1 EXTENT OF EXPOSURE

The extent of exposure (mean daily dose, cumulative dose, duration of exposure) to study drug will be summarized descriptively. Period 1 data with LEM5 or LEM10 will be summarized for: the number (percent) of subjects who completed 1 month (30 or more days), 3 months (90 or more days), and 6 months (180 or more days). Twelve-month (12-month) exposure with LEM5 or LEM10 will be summarized for: the number (percent) of subjects who completed 3 months (90 or more days), 6 months (180 or more days), 9 months (270 days), and 12 months (365 or more days) of dosing. (revised per Amendment 06)

Compliance will be calculated on the basis of number of tablets dispensed, lost and returned. Summaries will provide descriptive summary statistics and number (percentage) of subjects below 80%, between 80% and 120%, and >120%.

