3.6.2 Extent of Exposure

The extent of exposure (mean daily dose, cumulative dose, duration of exposure) to study drug will be summarized descriptively. Period 1 data with LEM5 or LEM10 will be summarized for: the number (percent) of subjects who completed 1 month (30 or more days), 3 months (90 or more days), and 6 months (180 or more days). 12-month exposure with LEM5 or LEM10 will be summarized for: the number (percent) of subjects who completed 3 months (90 or more days), 6 months (180 or more days), 9 months (270 or more days) and 12 months (365 or more days) of dosing.

The duration of exposure to study drug is defined as the date of last dose – the date of first dose date +1.

The exposure to Run-In Period placebo will be presented in the subject data listings only.

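### At 60% discontinuation the plan's own inputs give 96 elderly 12-month lemborexant completers, not the 100 that both documents say will be reached

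*Protocol*

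**What the plan says.** The last paragraph of Protocol 9.7.2 says the sample size also meets regulatory safety requirements. It takes discontinuation as high as 50% at Month 6 (150 remaining) and 60% by Month 12 (120 remaining in each treatment group). It concludes without condition that the trial will satisfy "the requirement for 100 subjects in each of the elderly and non-elderly age-groups to complete 12-months of treatment", the treatment being either dose of lemborexant, and adds that "420 total subjects would have completed 6 months of treatment of 5 mg or 10 mg lemborexant". SAP section 2 repeats the paragraph with the same figures and the same conclusion.

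Two other statements bear on it. On the age mix, Protocol 9.1 says "Approximately 40% of the population will be 65 years of age or older". On who receives lemborexant and for how long, the Protocol Synopsis says "subjects who previously received PBO will undergo a 2nd randomization to receive LEM5 or LEM10 for 6 months".

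On what counts as 12 months, Protocol 9.7.1.8.1 tabulates subjects with "12 months (365 or more days) of dosing", and SAP 3.6.2 has "9 months (270 or more days) and 12 months (365 or more days) of dosing". The Synopsis gives the duration of treatment as "Up to 17 days of PBO during the Run-In Period and up to 52 weeks of randomized treatment". SAP Tables 9 and 10 set the Month 12 target at study day 364. Footnote g to Protocol Table 3 says of the month used in the visit schedule: "Defined as a calendar month".

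**The concern.** The assurance is worded as a worst case: even at the discontinuation rates named, each age group reaches 100. Such a statement should follow from the retention figures beside it and the planned age mix. It follows for the non-elderly but not for the elderly, because placebo subjects who switch at Month 6 cannot complete 12 months of lemborexant.

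At stake is the reliability of a stated safety-exposure property in the older age group. Long-term safety over 12 months is one of the study's declared purposes (Protocol 7.2). A reader who relies on the sentence would believe the elderly requirement is secure at 60% discontinuation, when at nominal inputs it is slightly missed.

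The secondary point concerns how 12-month exposure will be counted. A subject dosed for exactly 52 weeks would finish planned treatment but would not appear in the row for 365 or more days.

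**Working it through.** **Inputs**

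- 900 randomised, 300 per group (Protocol 9.7.2), allocated approximately 1:1:1 (9.4.3), so 600 start on lemborexant.
- Discontinuation of 50% at Month 6 and 60% by Month 12 (9.7.2).
- Share aged 65 or over: about 40% (9.1).
- Former placebo subjects receive lemborexant in Period 2 only, for 6 months (Synopsis; 9.1.2.2).
- Assumption: the same discontinuation in both age groups. The documents give no rate by age.

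**The plan's own counts, reproduced**

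- Month 6: 300 x (1 - 0.50) = 150 per group.
- Month 12: 300 x (1 - 0.60) = 120 per group.
- Six-month lemborexant completers: 150 + 150 + 120 = 420.

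All three match. The 420 also shows how the paragraph treats the placebo arm: its 120 Month 12 survivors are credited with 6 months of lemborexant. The two-arm count for 12 months is therefore the plan's own reading.

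**12-month lemborexant completers at 60% discontinuation**

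- Total: 600 x 0.40 = 240.
- Elderly: 240 x 0.40 = 96, which is 4 below 100.
- Non-elderly: 240 x 0.60 = 144, which is met.

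Two other readings do not help. Counting all three arms gives 360 x 0.40 = 144 elderly, but treats 6 months of lemborexant as 12. Reading the requirement per dose gives 120 x 0.40 = 48 elderly per dose, further short.

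**Sensitivity of the expected elderly count**

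| Elderly share | Discontinuation by Month 12 | Calculation | Elderly completers |
|---|---|---|---|
| 35% | 60% | 600 x 0.35 x 0.40 | 84 |
| 40% | 60% | 600 x 0.40 x 0.40 | 96 |
| 45% | 60% | 600 x 0.45 x 0.40 | 108 |
| 40% | 55% | 600 x 0.40 x 0.45 | 108 |
| 40% | 50% | 600 x 0.40 x 0.50 | 120 |

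**Break-even for an expected 100**

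- Share, at 60% discontinuation: 100 / 240 = 41.7%.
- Elderly discontinuation, at a 40% share (600 x 0.40 = 240 elderly starting on lemborexant): 1 - 100/240 = 58.3%.

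**Chance of reaching 100**, if each subject completes independently (an assumption):

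- Nominal inputs: P(Binomial(240, 0.40) >= 100) = 0.32.
- Share at break-even (600 x 0.417 = 250 elderly): P(Binomial(250, 0.40) >= 100) = 0.52.
- Discontinuation at break-even: P(Binomial(240, 0.417) >= 100) = 0.53.
- Non-elderly (600 x 0.60 = 360 starting on lemborexant): P(Binomial(360, 0.40) >= 100) > 0.999.

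**Day count**

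- 52 weeks: 52 x 7 = 364 days, one short of the 365-day row. The SAP Month 12 target is also day 364.
- Calendar months: 12 months from Day 1 falls on study day 366. With the last dose the night before, exposure is 365 days in a non-leap year, which just qualifies.

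**The case against.** The strongest reply is that the miss lies within the tolerance of the inputs. The share, the total and the allocation ratio are all stated as approximate, 41.7% is still approximately 40%, and the range of 84 to 108 spans 100. The 60% is an outer bound, and at 50% there is a margin of 20. Protocol 9.1 also allows enrolment of younger subjects to be limited if the elderly share runs low. This is why the shortfall should be called marginal, and it makes the 35% case less likely. It does not rescue the sentence: the assurance is unconditional, it fails at the nominal values of the case it names, and the enrolment limit is optional and aims at about 40%, not 41.7%.

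The binomial figures can fairly be called secondary. The paragraph speaks of expected numbers, and a chance a little above one half is what any target set at its expectation gives.

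The day-count point is also open to challenge. The sample-size paragraph sets no day threshold, and completion is defined elsewhere by assessments through Period 2. Visit 15 has a window of 7 days either side, packs carry spare tablets, and the SAP windows run to day 371, so many subjects may pass 365 days. That is right, and it limits the point to wording that needs reconciling in one descriptive row. Finally, treatment completion by group is already planned, so an extra exposure row would be new only in its age split and is optional.

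**Conclusion.** The concern holds. With 300 per group, a 40% elderly share, 60% discontinuation by Month 12 and equal dropout by age, 96 elderly and 144 non-elderly subjects are expected to complete 12 months on lemborexant. The elderly half of the assurance is missed by 4; the non-elderly half is met comfortably. The result turns on modest changes in the inputs, so this is a marginal miss in a planning statement. The efficacy sample size and power do not change. The documents do not give the source of the 100-per-group requirement, so the regulatory consequence of 96 against 100 cannot be judged from them.

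The 52-week, day-364, calendar-month and 365-day wordings are inconsistent by a day or so and are not reconciled anywhere.

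**What to change.** In Protocol 9.7.2 and SAP section 2, replace the assurance with wording such as:

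> At 60% discontinuation by Month 12, 240 subjects are expected to complete 12 months of lemborexant (144 non-elderly and 96 elderly at a 40% elderly share, assuming equal dropout by age). An expected 100 elderly completers needs an elderly share of at least about 41.7% or elderly discontinuation of at most about 58.3%.

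Separately, reconcile the descriptions of 12 months in the Synopsis (Duration of Treatment), Table 3 footnote g, Protocol 9.7.1.8.1, SAP 3.6.2 and SAP Tables 9 and 10. Optionally, show the number completing the Month 12 visit on drug, by age group, beside the row for 365 or more days.

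The cost is one sentence in each document, a wording check and, if wanted, one descriptive table row. No extra subjects and no change to recruitment are needed. The only downside is a slightly less favourable statement.
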